14.5.1 Analgesic use

Rescue medication use over the treatment period will be listed for each subject.

14.6 Analysis of safety data

14.6.1 Extent of exposure

The number of subjects exposed to study treatment, and total IMP administered within each period and overall, will be summarised.

14.6.2 Adverse events

Adverse events will be coded using the Medical dictionary for regulatory activities (MedDRA) and summarised by system organ class (SOC) and preferred term (PT).

A summary of the number and percentage of subjects with the following adverse events will be prepared:

- All adverse events
- Serious adverse events
- Adverse events leading to premature discontinuation of IMP

- Adverse events by intensity
- Adverse events by relationship to IMP

All summaries of adverse events will include only treatment emergent adverse events (TEAEs). Refer Section 13.1 for adverse event definitions.

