Subjects will leave the clinic with their diaries and one dose of IMP (alternate treatment), instructions to take the dose within one hour of the onset of a migraine headache of moderate to severe intensity (NRS ≥ 4), but not less than 48 hours after last dose and instructions to complete the diaries as for Treatment period 1. No analgesics or antimigraine medication other than medications for routine prophylaxis not on the Prohibited medicines list may be taken within 24 hours prior to taking the dose of IMP. Rescue medication is permitted a minimum of 2 hours post dose.

The subject will be instructed to phone the clinic within one business day of taking the dose.

If the subject has not phoned the clinic, the subject will be phoned 14 days after Visit 3 to remind them to complete their diaries and to phone the clinic when the

dose has been taken.

Subjects will return to the clinic for Visit 4 within 5 business days, after taking the dose or a maximum of 28 days after Visit 3 if IMP has not been taken.

Visit 4

Subjects will return to the clinic with their diaries at completion of Treatment period 2.

Blood and urine samples will be taken for safety analysis. 12-lead ECG, vital signs, concomitant medications, targeted physical examination results and adverse events will be recorded. Subjects will be asked to complete assessments for Subject satisfaction of IMP Treatment period 2 and overall preference.

End of study, Visit 5

Subjects will be phoned 7 days after Visit 4 to review any new or changed adverse events or changes in concomitant medications.

Early withdrawal

An early withdrawal visit should be conducted within 7 days of the subject withdrawal, and/or a minimum 48 hours after last dose of IMP.

Subjects who are completing an early withdrawal visit will return with their diaries and IMP.

Blood and urine samples will be taken for safety analysis. 12-lead ECG, vital signs, concomitant medications, targeted physical examination results and adverse events will be recorded. Subjects will be asked to complete assessments for Subject satisfaction.

Statistical analysis

No formal statistical sample size estimation has been performed due to the exploratory nature of this study. Rather the sample size is based on clinical and practical considerations.

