14.4 Subject disposition

The total number of subjects will be summarised. The duration on study, and number of subjects terminating the study treatment early, along with the reason for early study treatment termination will also be summarised.

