### 11.1 Subject Disposition

Following categories will be summarised in subject disposition table:

- Subjects in FAS population – frequency (n)
- Subjects in Safety Population – frequency (n) and percentage (%) based on FAS
- Subjects in Per-Protocol Population – frequency (n) and percentage (%) based on FAS
- Subjects completed the study, subjects who attended each visit within each study period - frequency (n) and percentage (%) based on FAS; Early Termination will be summarised in period 2 irrespective of when the subject discontinued from the study.
- Subjects who terminated the study along with reasons - frequency (n) and percentage (%) based on FAS
- Study duration in days – n, mean and standard deviation, median, minimum, maximum

Note that FAS population will be displayed by planned treatment sequence and all other categories will be displayed by actual treatment sequence. Reasons for discontinuation will be sorted by descending order of frequency within the “Total” column.

In DDP: Table 14.1.1

Subject disposition, status of inclusion/exclusion criteria, status of unblinding, subjects excluded from analysis population along with reasons will be listed by subject.

In DDP: Listing 16.2.1.1, Listing 16.2.1.2, Listing 16.2.1.3 and Listing 16.2.3

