## 11.7 Extent of Exposure

Number and percentage of subjects exposed to IMP and number of subjects not exposed to IMP will be summarised by study period and treatment. Continuous summary statistics will be displayed for

total IMP administered in mg by treatment overall and within each study period. Number and percentage of subjects exposed and not exposed to IMP in any one of the periods or both will also be summarised by study period. The summary will be based on the FAS population.

The same will be repeated for Safety and Per Protocol populations.

In DDP: Table 14.1.7.1, Table 14.1.7.2 and Table 14.1.7.3

IMP administration and compliance data will be listed by treatment sequence, subject and treatment period for FAS population to include the IMP dispensing information.

In DDP: Listing 16.2.5

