#### **11.9.1.1 Overall Adverse Events**

The number and percentage of subjects and number of events will be summarised by AE status (new event or ongoing from the previous study period), treatment overall and within each study period for the following categories:

1. All adverse events reported
2. Treatment emergent adverse events (TEAEs)
3. Serious adverse events
4. Serious treatment-emergent adverse events
5. Related treatment-emergent adverse events
6. Related treatment-emergent serious adverse events
7. Suspected unexpected serious adverse events (SUSARs)
8. Treatment-emergent adverse events leading to death
9. Treatment-emergent adverse events leading to study discontinuation

The above categories and study periods will be classified as defined in section 10.10.

In DDP: Table 14.3.1.1 and Table 14.3.1.2

All adverse events will be listed by subject, system organ class and preferred term sorted by event start dates. Serious adverse events and deaths due to adverse events will be listed separately.

In DDP: Listing 16.2.7.1 to 16.2.7.3

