#### **11.9.1.2 Summary of Adverse Events by SOC and PT**

The number and percentage of subjects and number of events will be summarised by treatment overall and within each study period, system organ class and preferred terms. Percentages will be based on the safety population. System organ class and preferred term will be displayed in the descending order of frequency of total number of events in total LAT8881 60 mg group. All adverse events and all serious adverse events will be summarised by Pre-IMP and Post-IMP treatments. All treatment emergent and similar events will be summarised by study period, treatment and the event status (new event or ongoing from the previous study period).

The same will be repeated for all treatment-emergent AEs, treatment-emergent related AEs, serious AEs, treatment-emergent serious AEs, treatment-emergent related serious AEs, treatment-emergent AEs leading to discontinuation and treatment-emergent AEs leading to death.

In DDP: Table 14.3.1.2 to Table 14.3.1.4 and Table 14.3.2.1 to Table 14.3.2.5

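### The SAP replaces the protocol's counts of stopping IMP with counts of stopping the study, so a subject who declines dose 2 because of an adverse event but completes the visits appears in neither summary

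*Protocol*

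**What the plan says.** The protocol frames early stopping by treatment in two places. Section 14.6.2 lists, among the adverse event summaries, "Adverse events leading to premature discontinuation of IMP". Section 14.4 says that the "number of subjects terminating the study treatment early, along with the reason for early study treatment termination will also be summarised".

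The SAP frames it by study participation. Category 9 of the overall adverse event table in 11.9.1.1 is "Treatment-emergent adverse events leading to study discontinuation". The disposition table in 11.1 has "Subjects who terminated the study along with reasons", with no row for stopping treatment. The tables by system organ class and preferred term in 11.9.1.2 cover "treatment-emergent AEs leading to discontinuation and treatment-emergent AEs leading to death", without saying whether the study or the IMP is meant. The exposure table in 11.7 gives "Number and percentage of subjects exposed and not exposed to IMP in any one of the periods or both", without reasons.

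SAP 8.1, which records departures from the protocol's analyses, deals with hypothesis testing and the mixed model. It says nothing about discontinuation.

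**The concern.** In many trials stopping treatment and leaving the study nearly coincide. Here they can separate. Each period is one dose taken at home, so after dose 1 the only IMP left to discontinue is dose 2. A subject who never takes dose 2 is not expected to leave: the protocol synopsis has Visit 4 take place at "a maximum of 28 days after Visit 3 if IMP has not been taken". An undosed subject can therefore go through all remaining contacts.

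At stake is a descriptive tolerability count that the protocol specifies, in support of secondary objective 3 (safety and tolerability). If a subject refuses the second dose because of what followed the first, the protocol's summary would count it and the SAP's would not. A reader of the report would see zero in the discontinuation row and could not tell from the tables that a dose was refused for an adverse event.

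**Working it through.** There is no planned figure to reproduce, so the check sets the sections side by side and follows each kind of case through the SAP's rules.

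**Protocol against SAP**

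| Item | Protocol | SAP |
|---|---|---|
| Adverse events leading to stopping | IMP (14.6.2) | Study (11.9.1.1); object not stated (11.9.1.2) |
| Early termination with reason | Study treatment (14.4) | Study (11.1) |
| Undosed subjects | – | Counted by period, no reason (11.7) |
| What makes a completer | One dose in each period plus the follow-up visit (5.4) | Visit 5 completed (10.5), although SAP 4.2 repeats the protocol's definition |

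**Cases**

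1. The investigator judges that an adverse event requires the IMP to be suspended, or the stopping criterion is met. Protocol 7.11 and 12.1 then withdraw the subject from the study. The event falls in category 9 of SAP 11.9.1.1 and the reason in SAP 11.1. It is counted.
2. The subject decides not to take dose 2 because of an adverse event after dose 1, the investigator does not require suspension, and Visits 4 and 5 take place. Protocol 7.11 does not apply, because it turns on the investigator's opinion. Under SAP 10.5 the subject is a study completer. The event is absent from category 9 and the reason is absent from the disposition table. SAP 11.7 shows a subject not exposed in Period 2, in the same row as one who had no qualifying attack.
3. Protocol 7.11 applies but is not followed, and the subject stays in the study. The result is the same as in case 2.

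Only the treatment taken in Period 1 can be responsible in cases 2 and 3. Under SAP 10.10 an event before any dose is not treatment-emergent, and no dose follows dose 2.

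**Size of one case**

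- Against all planned subjects (26; protocol 5.4, SAP 4.2): 1/26 = 3.8%.
- Against those given that treatment first, assuming equal sequences: 26/2 = 13, and 1/13 = 7.7%.
- SAP adverse event percentages use the safety population, which may be below 26. The plan allows for up to 20% not treating in each period or dropping out: 0.20 × 26 = 5.2, about 5. If all 5 were never dosed, the denominator would be 26 − 5 = 21, and 1/21 = 4.8%.

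The 20% allowance covers every kind of non-treatment and dropout. The documents give no share for adverse events, so the expected number of cases cannot be derived.

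**The case against.** The best answer to this point is that the two terms nearly coincide by rule. Protocol 7.11 and 12.1 send every stop decided by the investigator or sponsor to study withdrawal, and protocol 5.7 lists a serious or significant adverse event among the possible reasons for discontinuation. That stands, and it confines the gap to cases 2 and 3. A reader might infer that the SAP misses every adverse-event-driven stop of IMP; the documents do not support that.

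It can also be said that SAP 11.9.1.2 leaves room for the protocol's meaning, since it does not restrict discontinuation to the study. This is fair, but 11.9.1.1 does restrict it, and the open wording is a reason to define the term. The data display plan, which might settle it, is not among the documents.

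Thirdly, the information is not lost. The adverse event still appears in the general tables by treatment, period, severity and relationship. By-subject listings cover IMP administration (SAP 11.7), the diaries (11.8.2.6) and telephone visits (11.9.3.4). With about 26 subjects, a careful reader could often work out that an attack went untreated after an adverse event. What is missing is the summary count and the stated reason, not the underlying data.

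Two further inferences should be set aside:

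- A reader might take this count for the main tolerability result. The safety endpoints in protocol 10.3 and SAP 7.3 do not name discontinuation.
- A reader might think that the reason for a missing Period 2 undermines the mixed model in SAP 11.8.1.3. A likelihood-based model allows missingness to depend on observed Period 1 scores, and the table rows proposed here would not change it.

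**Conclusion.** The point holds in a limited form. Two summaries that the protocol specifies have no explicit counterpart in the SAP, and the substitution is undeclared. The practical gap is one kind of subject: someone who, without an investigator or sponsor stop leading to withdrawal, does not take dose 2 because of an adverse event and completes follow-up. Each such subject moves the protocol's count by 3.8% of 26 planned subjects, or by about 7.7% of those given that treatment first. The second figure assumes equal sequences. Both are illustrations of one case, not forecasts, and if no such case arises the tables are unaffected. The correction is worth making before database lock because it restores what the protocol promised at little cost.

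**What to change.** - **SAP 11.9.1.1:** add a category for treatment-emergent adverse events leading to discontinuation of IMP, defined as dose 2 not issued or not taken because of the event. Attribute it to the treatment taken in Period 1 and state the denominator. Keep study discontinuation as a separate row.
- **SAP 11.9.1.2:** state that discontinuation covers IMP and study, shown separately.
- **SAP 11.1 or 11.7:** summarise IMP not taken, by period and reason (no qualifying attack, adverse event, subject decision, other).
- **SAP 8.1:** if the sponsor prefers to treat IMP and study discontinuation as the same, say so and justify it by protocol 7.11. That makes the change visible but leaves case 2 uncounted.

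Most of the data are already planned. Protocol 13.2 requires actions taken to be recorded for each adverse event, the diary shows whether an attack occurred, and unused capsules are counted on return (protocol 7.9, SAP 10.14). The capsule count shows that a dose was not taken but not why. Where the adverse event record and diary leave the reason open, site staff would need to ask when the unused bottle comes back. The cost is SAP wording, about two table rows, and possibly a slightly less favourable tolerability count.

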14.6.3 Clinical laboratory evaluations

Safety laboratory data (haematology, biochemistry, and urinalysis) will be summarised by visit and treatment. All laboratory data will be included in the data listings. In addition, a separate listing of laboratory data for subjects with clinically significant abnormal results will be prepared.

14.6.4 Other safety measures

Vital signs (body temperature, respiratory rate, heart rate, and blood pressure) will be summarised by baseline and treatment overall and for each treatment within the treatment sequence. Changes over time in vital signs will be summarised.

Physical examination data will be listed only.

The number and percentage of subjects receiving concomitant medications will be tabulated overall and by medication received.

15. Study management

15.1 Regulatory and ethical considerations

15.1.1 Regulatory compliance and ethical conduct

This study must be conducted in compliance with the study protocol, the requirements and obligations of the International Conference on Harmonisation (ICH) and Good Clinical Practice (GCP) guidelines, Integrated Addendum to ICH E6(R1): Guideline for Good Clinical Practice E6(R2),¹ the World Medical Association Declaration of Helsinki¹⁶ and its amendments and all applicable local guidelines, laws and regulations.

Investigators and other site personnel will undergo appropriate study-specific training during the study site initiation visit. Before initiation of the study at the site(s), the written approval / favourable opinion of the local and/or national independent ethics committee(s) and relevant health authority(ies) will be sought and obtained.

15.1.2 Ethics committee review

Prior to the initiation of the study, the protocol and associated documentation (including all materials used to recruit subjects for the study) must be given a favourable opinion by an ethics committee (EC). A copy of this written approval and any correspondence with the EC will be provided to the sponsor.

The investigator must obtain approval from the sponsor before potential subjects can undergo any study-specific screening procedures.

The investigator will comply with any additional requirements imposed by the EC. The investigator must submit progress reports to the EC according to local regulations and guidelines. The investigator must also provide their EC with any reports of SAEs from the study site in accordance with the EC's requirements and timelines.

15.1.3 Informed consent process

The investigator will ensure that the subject is given full and adequate oral and written information about the nature, purpose, possible risks and potential benefits of the study. Subjects must also be notified that they are free to discontinue from the study at any time. The subject should be given the opportunity to ask questions and should be allowed time to consider the information provided.

The subject's signed and dated informed consent must be obtained before conducting any procedure specifically for the study. The investigator must store the original, signed ICF with the subject's medical records. A copy of the signed and dated ICF must be given to the subject.

Subjects who are incompetent and unable to freely provide informed consent and subjects who are unable to read or speak English without the assistance of an interpreter will not be invited to participate in the study.

If new information arises during the study that may affect the safety of the subjects, the protocol and ICF will be amended as appropriate and submitted to the EC as outlined in Section 15.1.4. Following approval by the EC, subjects will be advised by letter of any safety related updates that may impact during the post-study period and be invited to discuss any concerns with the investigator. When applicable, subjects may be requested to re-consent to ongoing their participation in the study.

15.1.4 Protocol amendments

The signed, EC-approved protocol must not be changed without the agreement of the sponsor. If it is necessary for an EC-approved study protocol to be amended, the relevant EC and, if required, the local

regulatory authority must be informed and asked for its opinion as to whether a re-evaluation of the ethical aspects of the study is necessary.

The investigator must not implement any deviation from, or change to the protocol, without agreement by the sponsor and prior review and documented approval/favourable opinion of the amendment from the relevant EC, except where it is necessary to eliminate an immediate hazard to study subjects, or where the change(s) involve(s) only logistical or administrative aspect(s) of the study, for example, change in monitor(s) or change of telephone number(s).

If a protocol amendment requires a change to the Participant information sheet (PIS) or Informed consent form (ICF), approval of the revised PIS and ICF by the sponsor and EC is required before the updated document can be used.

Following approval, the sponsor (or delegate) will distribute new versions of amended documents (eg protocol, PIS, ICF) to the site.

15.1.5 Protocol deviations

No deviations from or changes to the protocol will be implemented without documented approval from the EC of an amendment, except where necessary to eliminate an immediate hazard(s) to study subjects or when the change(s) involves only logistical or administrative aspects of the study.

Any deviations from or changes to the protocol which were implemented to eliminate an immediate hazard and the proposed amendment, if appropriate, should be submitted to the EC for review and approval as soon as possible.

Should any protocol deviation occur, it must be reported to the study monitor as soon as is reasonably practical. If a major protocol deviation occurs, the investigator must notify the sponsor and the appropriate EC as soon as possible or as per local requirements.

All instances of noncompliance with the requirements of the Study protocol will be captured in a Protocol deviation log. The deviation and the reason for its occurrence must be documented, reported to the relevant EC (if required) and included in the clinical study report.

15.2 Quality control and quality assurance

15.2.1 Training of staff

Each individual involved in the study must be qualified by education, training and experience to perform his or her respective tasks.

Site staff may be trained at investigator meetings and initiation visits by the sponsor or their designees.

15.2.2 Study monitoring

The study will be independently monitored in accordance with ICH GCP¹ and applicable local regulations.

Before the start of the study, a study monitor appointed by the sponsor will evaluate the investigational site to ensure facilities are adequate and to discuss responsibilities with the site staff with regards to following the protocol and regulatory and ethical requirements.

During the study, the study monitor will regularly visit the site to monitor and confirm protocol, regulatory and ethical adherence, confirm data accuracy and provide information and support as needed.

The investigator is responsible for maintaining source documents. The investigator must agree to allow the study monitor direct access to all relevant documents at each monitoring visit, including electronic medical records, and to allocate their time and the time of their staff to the study monitor to discuss findings and any relevant issues.

Site staff will be provided with contact details for the study monitor and back-up persons in the event they have queries or require assistance.

15.2.3 Data management and quality control

The sponsor (or delegate) will be responsible for activities associated with the data management of this study. This will include setting up a database and data transfer mechanisms, along with appropriate validation of data and resolution of queries.

Data generated within this clinical study will be handled according to the relevant SOPs of the sponsor and/or their delegate(s). An electronic CRF (eCRF) will be created by the data management group for recording of the required data and integration into the study database. All data (including electronically available data, ie eCRF and laboratory data) will be integrated into a validated Data Management System with full audit trail capability (ie a computerised log of all subsequent changes to the data will be recorded). Automated checks will be made against the data to ensure completeness and consistency. The database and check programs will be validated before implementation. AEs will be coded using MedDRA and medications will be coded using the current version of the WHO drug dictionary.

Missing or inconsistent data will be queried via system generated queries to the investigator for clarification. Subsequent modifications to the database will be documented.

Data collection and entry into the eCRF will be completed by authorised study site personnel designated by the investigator. Appropriate training and security measures will be completed with the investigator and all authorised study site personnel prior to the study being initiated and any data being entered for any study subjects.

The eCRFs should always reflect the latest observations on the subjects participating in the study; therefore, the eCRFs are to be completed as soon as possible during or after the subject's visit. The investigator must verify that all data entries in the eCRFs are accurate and correct. If some assessments are not done, or if certain information is not available or not applicable or unknown, this should be indicated in the eCRF. The investigator will be required to sign off on the final clinical data.

During the study the study monitor will review the eCRFs and evaluate them for completeness and consistency. The eCRF will be compared with the source documents to ensure that there are no discrepancies. All entries, corrections and alterations are to be made by the investigator or designee.

The study monitor cannot enter data into the eCRFs. If corrections are needed, the responsible study monitor or data manager will raise a query and the appropriate investigational staff will be required to provide an answer. All queries and resultant data changes will have an electronic audit trail, meaning that the name of the investigational staff responding to the query, time and date stamp are captured.

The eCRF is considered a data entry form and should not constitute the original, or source document, unless otherwise specified. Source documents are documents used by the investigator or study site that relate to the subject's medical record, that verify the existence of the subject, the inclusion and exclusion criteria and all records covering the subject's participation in the study. They include, but are not limited to, laboratory reports, hospital records, subject files, etc.

eCRFs will be completed for subjects who have signed the ICF, are eligible for this study and have been enrolled in the study.

